At a more basic level, as noted above, we are studying the effects of targeting basic forms of gain control and integrative processes on higher-level perceptual and cognitive processes. We are including two intervention components (UE and CIT) in order to explicitly target both CS and PO because there is evidence that both aspects of visual function are impaired in schizophrenia AND that impairments in both are related to poorer functioning in multiple domains. Because this is the first controlled study of perceptual remediation of these functions in schizophrenia, we wish to remain agnostic regarding whether the combined treatment (UE&CIT) will be more effective than either UE or CIT alone, although we anticipate that the combination may have additive or synergistic effects on one or both levels of vision. By assessing improvements related to the single treatment (UE or CIT) AND to the combined intervention at each level of vision, we will be able – at the end of the project – to provide a strong initial statement regarding the important question of differential and combined intervention effects. Future clinical trials will determine whether there are subgroups of individuals with schizophrenia (e.g., those who are more impaired on CS or PO at baseline) who are especially likely to benefit from these interventions. This is not a specific aim for this initial clinical trial because even people without visual impairment can improve their visual functioning; however, our data will allow us to assess the degree to which improvement is a function of baseline CS and PO.

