Aims: (i) To replicate and extend R61 results supporting initial visual target engagement using the optimal R61 treatment, in a new and larger sample; and (ii) to determine if visual target engagement is associated with improvements in specific cognitive (i.e., visual working memory, visual learning and memory, reading) and social cognitive (*i.e.*, facial emotion recognition) outcomes, as well as with changes in functional capacity. Study design: The R33 will be a two parallel-arm RCT comparing the optimal R61 treatment to the control (ACCT) treatment. 100 subjects will be enrolled over 3 years, 50 from NKI and 50 from Rutgers. Visual and clinical outcome assessments will be conducted at baseline, and at intervals determined based on R61 results, including a 6-month follow-up (with attrition considerations and procedures identical to the R61 (see D.3). **Randomization:** Subjects will be randomly assigned, within site, to the optimal or control treatment in a ratio of 1:1. Treatment assignment for eligible subjects will occur after completion of baseline testing, to avoid bias. Assessments: Visual Targets and Cognitive, Social Cognitive, and Functional Capacity. No matter which intervention is used for the R33, visual tests will include both tests of CS, and both tests of PO used in the R61. See below (section D.6.c) for descriptions of the cognitive, social cognitive, and functional capacity measures. **Data analysis:** An intention to treat approach to data analysis will be used in this clinical trial. For all analyses. statistical significance will be defined as p < 0.05, unless specified otherwise. Bonferroni corrections will be applied to multiple testing, as appropriate. H1: The optimal R61 treatment will be more effective than the control treatment (ACCT) in improving CS and/or PO test scores (to be determined based on the R61 outcome). This will be tested using a linear mixed effects model in which the values of the target(s) at each time point are modeled as a function of treatment group (experimental, control), time, time x group, and potential moderators and mediators (e.g., age). We will use Akaike's Information Criterion (AIC) as the deciding metric to determine the optimal model to account for within-subject correlations between repeated measures (e.g., autoregressive of order 1, AR(1), which assumes stronger within-person correlation for measurements closer in time, or other structures). If the time x group interaction is significant, we will use model-based estimation procedures to estimate the magnitude of the effect. We will also explore differential effects of the treatment on CS vs. PO. H2: Improvements in visual processing, as observed in CS and/or PO (based on R61 results), will be related to changes on specific cognitive (i.e., visual working memory, visual learning and memory, reading), social cognitive (i.e., emotion recognition), and functional capacity measures. We will assess correlations between visual target scores and cognition, social cognition, and functional capacity, and also evaluate whether changes in the target(s) either mediate or moderate treatment effects on these outcomes. An approach and computational tool described by Hayes will be used to model any mediation and /or moderation effects, including indirect effects in models that involve mediation. Sample size determination: The sample size for the RCT in the R33 phase was selected to ensure sufficient power to detect medium effects of the experimental intervention on the target(s). For Aim 1 of the R33, 50 subjects per condition allows 80% power for a 2-tailed test with  $\alpha$ =0.05 to detect d=0.57. For Aim 2, with n=50 in the active perceptual training group, correlations of at least r=0.38 between changes in performance on target measures (CS and/or PO) and changes in cognitive, social cognitive, and functional capacity can be detected with 80% power using a 2-tailed test with  $\alpha$ =0.05. Also, for Aim 2, n=50 (i.e., active perceptual intervention only) allows for detecting a correlation of r=0.43 when making a strict Bonferroni adjustment for 3 outcomes (2-tailed  $\alpha$ =0.017), and r=0.51 when correcting for 15 outcomes (2-tailed  $\alpha$ =0.003). In accordance with instructions that the R33 "should not be powered as a strong test of clinical efficacy...", our focus on effect size is exploratory and not confirmatory. We will use our observed effect sizes to power a later RCT. D.5 Interventions

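### R33 H2 plans to test change in CS or PO as a moderator of the treatment effect, but that change is a post-randomisation response to treatment and cannot identify effect modification

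*Combined protocol and SAP*

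**What the plan says.** The sentence is in the combined protocol and SAP, section D.4 (R33 Phase), data analysis for H2. After correlations between visual target scores and the cognitive, social cognitive and functional capacity outcomes, the plan will "evaluate whether changes in the target(s) either mediate or moderate treatment effects on these outcomes". A cited regression tool "will be used to model any mediation and /or moderation effects, including indirect effects in models that involve mediation".

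Two other statements in D.4 fix what kind of variable the change score is:

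- Timing: "Treatment assignment for eligible subjects will occur after completion of baseline testing, to avoid bias".
- Expected response to treatment, under H1: "The optimal R61 treatment will be more effective than the control treatment (ACCT) in improving CS and/or PO test scores".

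D.4 does not limit R33 moderators to baseline variables. For H2 it names no confounders and no causal assumptions. Elsewhere the document treats moderation in the usual way. D.3 plans baseline characteristics as moderators in the R61. Section B says that "our data will allow us to assess the degree to which improvement is a function of baseline CS and PO". D.6.b collects acuity to see whether it moderates training effects. Those passages are sound and are not further instances of the problem.

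**The concern.** A moderator is a characteristic that defines subgroups within which the randomised arms can still be compared. Target change does not do this. A control patient whose CS rises by a given amount without visual training is a different kind of patient from a trained patient with the same rise. Conditioning on the change breaks the randomised comparison, and the product of arm and change then mixes any real effect with the selection this creates.

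The same variable is also offered as the mediator. The plan's either/or wording leaves open that a significant product term would be reported as a finding about who benefits. The R33 exists to link target engagement to function, and its observed effect sizes are to inform a later trial, so a spurious moderation result could misdirect that design.

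**Working it through.** **Inputs from D.4.** "100 subjects will be enrolled over 3 years, 50 from NKI and 50 from Rutgers", and "Subjects will be randomly assigned, within site, to the optimal or control treatment in a ratio of 1:1", so 100 / 2 = 50 per arm. For the test level, "statistical significance will be defined as p < 0.05, unless specified otherwise". The detectable effect on the target is d = 0.57 at 80% power, two-sided.

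**The plan's own figure.** Noncentrality = 0.57 × √(50/2) = 2.85. The normal approximation gives Φ(2.85 − 1.96) = Φ(0.89) = 81.3%, and the noncentral t with 98 df gives 80.6%. The stated 80% is reproduced, and nothing below changes it.

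**Logic.** (1) Assignment follows baseline testing, so any change score is post-randomisation. (2) H1 says treatment moves it. (3) The proposed moderator is therefore a consequence of arm, and the arm-by-change coefficient is not a contrast of randomised groups. This holds at any sample size.

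**How a spurious interaction arises (assumed model).** Let control target change M have SD 1 and let the outcome change Y have SD 1. They correlate at r only because something unmeasured drives both. In the active arm, M is shifted by 0.57 and has extra between-person response of SD s, unrelated to Y. Training has no effect on Y. Then:

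- slope of Y on M in control = r
- slope in active = r / (1 + s²)
- interaction = −r s² / (1 + s²), although no effect exists

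Example, r = 0.38 and s = 1: the slopes are 0.38 and 0.38 / 2 = 0.19, a false interaction of −0.19. The apparent arm effect at change m is 0.19(m − 0.57) − 0.38m. At m = −1 this is −0.298 + 0.38 = +0.08. At m = +1 it is 0.082 − 0.38 = −0.30. The truth is 0 at both.

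**Rejection rate of the arm × change term** (least squares with arm, change and product; 50 per arm; two-sided 0.05; 20,000 simulated trials per cell):

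| r (assumed) | s = 0 | 0.3 | 0.5 | 0.7 | 1.0 |
|---|---|---|---|---|---|
| 0.20 | 4.8% | 5.0% | 5.6% | 6.3% | 8.8% |
| 0.38 | 5.0% | 5.6% | 7.1% | 10.8% | 20.3% |
| 0.50 | 5.4% | 5.7% | 8.9% | 15.7% | 34.4% |

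With r = 0 the rate is about 5% at every s. With a baseline variable of the same prognostic strength as the moderator it is about 5% at every r.

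**The case against.** **The inflation rests on inputs the documents do not give.** This is correct. It needs both an unmeasured common cause and more variable target change in the active arm. Without either, the rate is nominal, and with modest extra variance little happens. The value r = 0.38 matches the plan's detectable correlation for Aim 2, but that is a power figure for the hypothesised link, not an estimate of confounding. The error rates are illustrations. The invalidity of the estimand does not depend on them.

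**The wording may be loose.** D.4 gives no model equation, and an arm-by-mediator term is legitimate inside a mediation model under stated assumptions. But the text offers moderation as an alternative to mediation, with no such assumptions, so it needs correcting even if a mediation model was meant.

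**Relabelling the term changes nothing.** This is also right. Outcome on arm, change and their product is the same regression under either name, with the same bias, so the correction must include assumptions, adjustment and sensitivity analysis.

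**It is exploratory.** D.4 describes its effect-size work that way, and the H2 analysis given a power statement is the correlation. That lowers the priority. It does not give the coefficient the meaning claimed for it.

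**Stronger readings that the documents do not support.** A reader might take the bias in the arm coefficient at fixed target change (with equal variances, −0.57 × 0.20 = −0.11 to −0.57 × 0.38 = −0.22 SD) as evidence against moderation in particular. It is mediator-outcome confounding, and would equally affect the direct effect in a mediation analysis. A reader might also infer that the artefact would make training appear to help those whose vision improved most. In the model above it runs the other way, and its sign depends on which arm is more variable.

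**Conclusion.** The point holds in a limited form. As written, moderation by change in CS or PO is not a valid test of effect modification, on the plan's own statements about timing and expected effect. A false-positive result is possible but not inevitable: near 5% with equal variances, about 5 to 9% at added SD 0.3 to 0.5, and about 6 to 35% at added SD 0.7 to 1.0, for an assumed shared-cause correlation of 0.2 to 0.5 and no true effect on the outcome. A reader should not infer that the R33 as a whole is compromised. The H1 test, the planned correlations, the sample size and the R61 go/no-go rule do not use this analysis. It is a low-to-moderate priority correction to an exploratory analysis.

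**What to change.** In D.4, H2:

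1. Delete the words 'or moderate' as they apply to change in the target. State that R33 moderator tests use baseline variables only: baseline CS, PO and acuity.
2. Analyse target change only as a mediator, using both arms. An arm-by-mediator term may be included in that model but is not to be reported as effect modification.
3. State the no-unmeasured-confounding assumption for mediator and outcome, adjust for measured baseline confounders including baseline target and baseline outcome, and add a sensitivity analysis for mediator-outcome confounding.

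The first item restores the nominal error rate for moderator tests. The third is needed because moving the product term into a mediation model does not by itself remove the bias, and adjustment reduces it only as far as the common causes are measured. The cost is a few sentences of analysis text and a little more analysis work. No new data, visits or patients are needed.

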# D.6 Assessments

Standardized protocols including written instructions and scripts will be used at both sites for each test. VEPs will be obtained using an EvokeDx device with the active electrode over the occipital lobe (Oz). EvokeDx has FDA 510(k) clearance for assessment of visual neural function. It generates the stimuli, records and analyzes the electrophysiological signals, and stores the data. Psychophysical CS will also be performed using the EvokeDx, which utilizes an organic LED display that enables accurate linearization of the voltage-to-luminance relationship through customized gamma correction so that precise specification of contrast can be achieved. These features, in addition to the carefully calibrated amplifiers contained in the system, afford high reliability/reproducibility of stimulus presentation and VEPs collected with multiple EvokeDx devices, which is critical when testing at multiple sites. The same stimulus parameters and testing conditions will be used at the Rutgers and NKI sites, and automated luminance calibration will be performed monthly at each site using the photometric device provided with the EvokeDx by Konan medical. Amplifier settings will be as follows: gain=20K, bandpass filter=0.5–100 Hz. It should also be noted that an earlier version of the system now provided by Konan equipment for assessing CS was successfully used in a prior multi-site trial. The JOVI has also been successfully used in prior multi-site studies. For all luminance and contrast calibrations of monitors used for PO assessments, and for UE and CIT training, a photometer will be used initially and annually, and Spyder 3 Elite software will be used weekly, with gamma set to 1.0 (i.e., linearized).

# D.6.a Diagnostic and Clinical Assessments for R61 and R33

Diagnosis: The Structured Clinical Interview for DSM-5 (SCID-5) and all available clinical information will be used to assign a consensus diagnosis.

Verbal IQ estimate: WRAT-III, reading subtest. The recognition and pronunciation of printed words is particularly resistant to the effects of deterioration associated with brain disease and is considered to be an estimate of premorbid IQ.

Symptoms: The Positive and Negative Syndrome Scale (PANSS) assesses the presence and severity of symptoms commonly found in schizophrenia; it is a semi-structured interview. There are a total of 30 items. Suicidal Ideation and Behavior: The Columbia-Suicide Severity Rating Scale (C-SSRS). This will allow the investigators to determine if participants have suicidal ideation or behavior. This will be used at baseline and at the end of the intervention. Crisis service staff will be contacted at once if suicidal ideation or behavior is found. Reliability assessment: For all clinical and cognitive assessment measures, research assistants from both sites will be trained by [name] at the beginning of the study, and through annual booster sessions. Training will follow our typical protocol and involve didactic training, group viewing and discussion of training videos for the interview measures and all individual items, and individual rating of additional videos until reliability criteria are achieved. These are: 1) for PANSS - intraclass correlations (ICC) of 0.80 or higher between each rater and our existing gold standard, and an overall group ICC of 0.80; and 2) for SCID and C-SSRS, kappas of 0.80 or higher between each rater and our gold standard and between each rater pair. Trainees will also observe more senior interviewers administering these clinical measures (for other ongoing studies), and then be observed administering these measures by [name] or [name] before they conduct assessments for this study on their own, to ensure appropriate skill level in working with patients. Other: Smoking: Recent and typical tobacco use, and tobacco use disorder will be assessed with a smoking history and the Fagerström Test for Nicotine Dependence.

# **D.6.b Visual Targets**

Contrast Sensitivity: CS functions will be obtained by presenting 5 horizontal sine-wave gratings at the following SFs: 0.5, 1, 4, 7, and 21 cycles per degree. Spatial frequency is the number of pairs or cycles of light and dark bars in 1 degree of visual angle, expressed as cycles/degree, with fewer pairs corresponding to lower SF. Each grating will be presented for 32 milliseconds. An up-and-down transformed response method will be used to obtain contrast thresholds with a criterion of 70.7% correct responses for each SF. The mean of 10 reversals will be used to obtain thresholds. Presentation of the different SF gratings will be interleaved in a random order. A spatial 2-alternative forced-choice procedure will be used. Gratings will be presented on either the right or left side of the screen, and the participant's task is to determine on which side the gratings appeared. Results will be plotted as CS (which is the reciprocal of threshold) vs. SF. Increased CS indicates better performance. Participants will be tested binocularly after being light-adapted to the background luminance of the display for 15 minutes. Test re-test reliability of this measure in a group of 15 controls and 31 patients (tested at the [name] lab at NKI) was an ICC of .76 at 0.5 cpd and .67 and 1 cpd. The test-retest reliability is weaker at the peak SF of 4 cpd (.25) and improves with higher SFs (ICC=.69 for 7 cpd and .57 for 21 cpd). The target variable is the average CS for the two LSFs (0.5 cpd and 1 cpd). We expect to see more of an effect of the remediation on LSF, but we will also assess CS at the other SFs, and specifically compare LSF

results to results at 7 cpd, which also has high reliability, to determine if effects are LSF-specific. VEP Contrast Responses: This VEP technique was developed by [name] and colleagues and has been used in studies of schizophrenia , autism^82, and glaucoma detection. The response measures are quickly and easily obtained, requiring no behavioral response from the participant. Parameters to be used have been optimized in our studies of schizophrenia. Steady-state VEPs are elicited to checkerboard patterns that are luminance-modulated sinusoidally (~12 Hz) with contrast increases in 7 discrete octave steps. Each

ure 4: VEP Contrast stimuli examples				
4%	8%	16%	32%	64%

[figure not shown]
step is ~1.6 sec in duration to yield an entire contrastresponse function in less than 10 seconds (Fig. 4). The initial step has 0% depth of modulation (DOM) and this is followed by steps of 1, 2, 4, 8, 16, and 32% DOM. The set of steps is presented 10 times. In the contrast response function, as the DOM rises, the signal-to-noise ratio (SNR) increases from below a value of 1 to a value

greater than 1. To obtain the contrast at which SNR=1 (i.e., the contrast threshold), linear interpolation will be done for the first two consecutive contrasts (DOMs) at which SNR is less than one and then greater than one

. Test-retest reliability of low-contrast VEP responses in schizophrenia (N=32) is good (ICC=0.70; [name] lab, unpublished data). In addition, the 95% confidence regions for the 10 runs per person show good reliability within an individual. [name] has observed a within-subjects correlation of r=.41, (p<0.001; N=74) between indices from these VEP and psychophysical CS assessments.

Jittered Orientation Visual Integration (JOVI) Task: Stimuli consist of oval contours, made up of 18 Gabor elements separated by 1° of visual angle, that either point left or right (Fig. 3). The contours are embedded in 298 distractor Gabors. Difficulty is manipulated by increasing the degree of orientational jitter of the Gabors making up the contour. Jitter levels will be 7°, 9°, 11°, 13°, and 15°, as in recent studies. Trials will be blocked according to the amount of orientational jitter, with 12 trials per block. Blocks will be presented in increasing order of difficulty, with each block presented 4 times for a total of 240 trials (4 repetitions x 5 blocks x 12 trials). In addition, each block will contain 4 catch trials in which a contour with no orientational itter is presented without background elements, or is presented with background elements but with a line drawn along the contour. These trials are included to identify subjects who respond randomly or who are not paying adequate attention to the task. As in past studies, only subjects who obtain 75% or higher accuracy on these trials will be included in data analyses. Each stimulus is shown for 2 seconds, followed by a 1 second inter-stimulus interval. The participant presses a right or left arrow key to indicate the direction of the contour. There will be practice trials prior to the task, using the format in past studies. This task was optimized for use with participants with schizophrenia in a previous 5-site study, which found good test-retest reliability. The dependent variable is number correct, corrected for guessing (to equate with subjects who respond when unsure of the correct answer, who will be right 50% of the time).

Ebbinghaus Illusion Task. On each experimental trial, subjects are shown two target circles—one on the left of the screen and one on the right, and their task is to indicate which is larger. On half the trials, these

circles are presented by themselves (i.e., the no-context condition). On the other half, the targets are surrounded by larger or smaller circles that either *facilitate* perceiving the true size difference of the target circles (helpful condition: the larger inner circle is surrounded by smaller circles, making it appear larger than its actual size, and the smaller inner circle is surrounded by larger circles, making it appear smaller than its actual size, and these effects combine to amplify the real size difference between the target circles: see Fig. 5. where the target circle on the right is 2% larger in each of the 3 panels), or hinder perceiving the true size difference (misleading condition: the larger inner circle is surrounded by larger circles, making it appear smaller than its actual size, and the smaller inner circle is surrounded by smaller circles, making it appear larger than its actual size). Stimuli remain on the screen until the subject responds or for 2 seconds (whichever occurs first). If a response is not recorded within 2 seconds, the trial is recorded as a guess (0.5 correct). Trials are separated by 200 msec. The two target circles always differ in actual size and this size difference varies in magnitude across trials. The order of trial types is randomized for each subject, as is the side on which the larger inner circle appears on each trial. In total, the task contains 192 trials, and typically takes 7 minutes. The key metric from this task is the difference between the helpful and

misleading conditions, controlling for no-context performance, or: [(Helpful – no context) – (misleading – no context)]. Reduced grouping is reflected in scores closer to 0.

Visual Acuity: While not a target for this study, acuity will be assessed to determine whether it moderates the effects of UE and/or CIT. We will use ETDRS charts, which are the "gold standard" for acuity testing. **D.6.c Other Outcome Measures for R33** 

MATRICS Consensus Cognitive Battery (MCCB): The MCCB assesses multiple cognitive domains: Speed of Processing, Attention/Vigilance, Working Memory (visual and verbal), Verbal Learning, Visual Learning, Reasoning and Problem Solving, and Social Cognition. The ICC for the MCCB composite score was 0.9 in the initial validation study and has been similarly high in multisite clinical trials. Outcomes are T-scores for each of the domains and the composite score (number of scores=8). In addition, exploratory analyses will assess whether treatment effects on **visual** working memory and **visual** learning are stronger than for non-visual memory and learning subtests.

Minnesota Low-Vision Reading Test (MNREAD): This test assesses reading speed ability. The charts contain 19 English sentences (60 characters each) with print sizes ranging from 1.3 to -0.5 logMAR at a distance of 16 inches (0.41 meters). Participants are instructed to read each sentence aloud as quickly and as accurately as possible. Outcomes are reading acuity, speed, and critical print size (number of scores=3). The MNREAD is resistant to practice effects and has strong test-retest reliability.

Penn Emotion Recognition Test (ER-40): This computerized task comprises 40 photographs of actors expressing one of 4 basic emotions (happiness, sadness, anger, fear) or a neutral expression. The outcome variable is total percent correct (number of scores=1). The ER-40 has been used widely including in multi-site studies (e.g.,). The ER-40 demonstrates sound convergent and discriminant validity and good test-retest reliability in participants with schizophrenia [ICC=.75].

University of California, San Diego Performance Based Skills Assessment, 2nd Edition (UPSA-2): This is a performance-based measure of the extent to which participants are capable of performing specific living skills such as household chores, communication, finance, transportation, and planning recreational activities. We will use the total score, which ranges from 0 to 100 (number of scores=1). Test-retest reliability is 0.63-0.80 over periods of up to 36 months. UPSA scores significantly predict residential independence.

**D.7 Clinical Research Data Management:** The Innovative Clinical Research Solutions (ICRS) group at NKI will conduct data management and data quality assurance for this study. The ICRS has been providing data management support for research studies for over 35 years, including for numerous schizophrenia studies funded by the NIMH. ICRS will develop all study Case Report Forms to standardize data collection. A comprehensive web-based data acquisition and management system, Acquire, will be programmed to process, edit and store all study data in a centralized database. ICRS personnel will implement rigorous data editing/validation using the Acquire system to ensure the highest possible level of data accuracy. ICRS personnel will review and monitor the completeness and accuracy of study data throughout the study, and deliver locked data sets to [name] at the end of both the R61 and R33 phases.

**D.8 Combined Expertise of the Research Team:** Drs. [name] and [name] have over 30 and 20 years of experience, respectively, in vision research in schizophrenia, expertise and publications in general and social cognition, track records of recruitment and assessment of individuals with schizophrenia for NIMH grants, and a track record of working and publishing together. Their respective foci on CS ([name]) and PO ([name]) provides particular synergy for this project. In addition, [name] has delivered cognitive remediation interventions for schizophrenia patients since 1994. [name] is an expert in perceptual learning and in development of scientifically principled brain games such as UE. [name] has over 30 years of experience in designing and analyzing data from longitudinal efficacy and multi-site data. Drs. [name] and [name] are experienced in clinical trial project management and in cognitive and clinical assessment of individuals with schizophrenia. [name] directs the NKI ICRS group, with 35+ years of experience in data management.

**D.9 Governance and Organizational Structure for Conducting Study within Specified Timelines:** Drs. [name] and [name] will be PIs of the overall grant and will be responsible for its implementation, progress, data collection, supervision, coordination, and fiscal management. Drs. [name], [name], and [name] will have primary responsibility for the guidance and fiscal management of relevant aspects of the study at their respective institutions. [name] will lead weekly calls with key personnel to ensure that all timeline goals are met. He will also lead weekly data management calls with ICRS personnel and all research assistants. **D.10 Feasibility of the Approach**: All of the elements are in place to carry out recruitment, remediation, and data analysis in a timely manner. Rutgers and NKI have on-site clinics that will be used for recruitment and treatment of patients, as in many past studies. Both sites have personnel trained in use of all measures. The UE program is fully developed and tested, and the CIT training program is currently in use in an initial study at Rutgers. Target and clinical outcome measures already exist. The ICRS data management group is in place.
